**Table 2: Simulation Estimates for Power and Type 1 Error for Various Mortality Rates**

Mortality Rates			Probability to Reject H 0 for		
PLB	5 mg BID	15 mg BID	5 mg BID	15 mg BID	Either RUX
60%	60%	60%	0.015	0.016	0.027
60%	60%	40%	0.012	0.873	0.873
60%	50%	40%	0.268	0.865	0.866
60%	40%	40%	0.868	0.872	0.940
60%	40%	30%	0.861	0.998	0.998

Note: For the simulation, investigational site was drawn from an integer uniform distribution (1, 2, ..., 10) and probability (ARDS severe) = 0.5, fitting a mixed logistic regression model with no direct effects for the ARDS severity or site.

Enrollment was halted and SAP Amendment 3 removed the interim analysis. The final analysis will be performed using all randomized participants enrolled at the time of SAP Amendment 3, which is 211 participants.

### 3.4. Schedule of Assessments

Refer to Protocol Amendment 1 dated 02 JUN 2020 for a full description of all study procedures and assessment schedules for this study.

## 4. DATA HANDLING DEFINITIONS AND CONVENTIONS

### 4.1. Scheduled Study Evaluations and Study Periods

#### 4.1.1. Day 1

Day 1 is the date that the first dose of study drug (ruxolitinib/placebo) is administered to the participants.

For randomized participants not treated with any study drug, Day 1 is defined as the date of randomization.

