12.4. Statistical Analyses

12.4.1. Primary and Secondary Analysis

Unless otherwise noted, all statistical comparisons of each ruxolitinib treatment groups will be performed as pairwise comparisons against placebo. See Table 10 for analyses of primary and secondary endpoints.

Endpoint	Statistical Method	Analysis Population	Primary (P) or Supportive (S)
Primary Endpoint			
Proportion of participants	Logistic regression with treatment	ITT	Р
who have died due to any cause through Study Day 29.	group, ARDS severity (mild/moderate vs severe), gender (male or female) as fixed covariates, and investigational site as a random effect. Wald test for treatment group regression coefficient = 0. Estimation: Odds-ratio for treatment effect and associated 95% CI.	РР	S
Overall survival up to Day 29 determined from the date of randomization until death due to any cause	Inference: Cox proportional hazards model including treatment group, ARDS severity (mild/moderate vs severe), and gender (male or female) as fixed covariates, and investigational site as a random effect. Estimation: Kaplan-Meier.	ITT	S

 Table 10:
 Analyses of Primary and Secondary Endpoints

Endpoint	Statistical Method	Analysis Population	Primary (P) or Supportive (S)
Secondary Endpoint			
Improvement in the	Proportional odds model including	ITT	Р
COVID-19 ordinal scale at Day 15 and 29	treatment group, ARDS severity (mild/moderate vs severe), and gender (male or female) as fixed covariates, and investigational site as a random effect.	РР	S

Table 10: Analyses of Primary and Secondary Endpoints (Continued)

All other secondary endpoints will be tabulated by summary statistics.

The primary endpoint will also be compared between the treatment groups within each of the following subgroups. In the event that any subgroup category has fewer than 10 participants, the subgroup in question may be excluded.

- ARDS severity: mild/moderate versus severe
- Gender: male or female
- Age group: < 18 years, 18-64 years, or ≥ 65 years
- Baseline CRP: $\leq 100 \text{ mg/L or} > 100 \text{ mg/L}$
- D-dimer at baseline: $\leq 1000 \text{ ng/mL or} > 1000 \text{ ng/mL}$
- Ferritin at baseline: $\leq 300 \text{ ng/mL or} > 300 \text{ ng/mL}$
- Race: White/Caucasian, Black/African-American, Asian, American-Indian/Alaska Native, Native Hawaiian/Pacific Islander, or Other
- Ethnicity: Hispanic/Latino, Not Hispanic/Latino, or Other
- Hours of mechanical ventilation at baseline: ≤ 48 hours or > 48 hours

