**Table 1: Objectives and Endpoints**

Objectives	Endpoints
Primary	
To evaluate the 28-day mortality rate of ruxolitinib 5 mg BID + SoC therapy and ruxolitinib 15 mg BID + SoC therapy compared with placebo + SoC therapy in participants with COVID-19–associated ARDS who require mechanical ventilation.	Proportion of participants who have died due to any cause through Study Day 29.
Secondary	
To evaluate the efficacy of ruxolitinib 5 mg BID + SoC therapy and ruxolitinib 15 mg BID + SoC therapy compared with placebo + SoC therapy on in-hospital outcomes in participants with COVID-19–associated ARDS who require mechanical ventilation.	At Day 29, the number of ventilator-free days, ICU-free days, oxygen-free days, vasopressor-free days, and hospital-free days will be summarized by treatment group.
To evaluate the efficacy of ruxolitinib 5 mg BID + SoC therapy and ruxolitinib 15 mg BID + SoC therapy compared with placebo + SoC therapy using a 9-point ordinal scale at Study Days 15 and 29 in participants with COVID-19–associated ARDS who require mechanical ventilation.	Ordinal scale: 
 
• Percentage of participants with at least 2-point improvement in clinical status at Day 15 and at Day 29.
 
• Percentage of participants with at least 1-point improvement in clinical status at Day 15 and at Day 29.
 
• Time to improvement from baseline category to earliest 1-point improvement in the ordinal scale.
 
• Percentage of participants in each 9-point ordinal scale category at Day 29.
 
• Mean change in the 9-point ordinal scale from baseline to Days 15 and 29.
 

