#### 4.1.2. Study Day

If a visit/reporting date is on or after Day 1, then the study day at the visit/reporting date will be calculated as

$$\text{Day \#} = (\text{visit/reporting date} - \text{Day 1 date} + 1).$$

If the visit/reporting date is before Day 1, then the study day at the visit/reporting date will be calculated as

$$\text{Day \#} = (\text{visit/reporting date} - \text{Day 1 date}).$$

A study day of -1 indicates 1 day before Day 1.

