#### **5.3.2. Intent-to-Treat Population**

All participants who are randomized will constitute the ITT population. Treatment groups for this population will be defined according to the treatment assignment at the time of randomization regardless of the actual study drug the participant might take during his/her participation in the study.

The ITT population will be used for the summary of demographics, baseline characteristics, participant disposition, and analyses of all efficacy data.

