#### **5.3.3. Per-Protocol Population**

The PP population comprises the subset of subjects in the ITT population who are compliant with requirements of the clinical study Protocol, including the following:

- Continued to meet all eligibility criteria on Study Day 1.
- Initiated correct randomized therapy within the Protocol-specified window.
- Did not significantly deviate from the Protocol in terms of missed study assessments, noncompliance with randomized therapy, or prohibited concomitant medications.

The PP population will be used in a supportive sensitivity analysis for the primary efficacy endpoint.

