#### **7.4.2.2. Improvements and Changes in COVID-19 9-Point Ordinal Scale**

The number and percentage of participants with a 1-point improvement at Days 15 and 29 will be tabulated and summarized by treatment group. A logistic regression model will be used to model the probability of such an improvement that includes treatment group and ARDS severity (severe vs mild/moderate) as fixed covariates and investigational site as a random effect. A similar summary will be used for 2-point improvements at Days 15 and 29.

The time from randomization to first 1- (or more) point improvement in the COVID-19 9-point ordinal scale will be derived. Participants who never improve on-study will be censored at their last assessment or Study Day 29, whichever is earlier. A Kaplan-Meier analysis will be used to describe the time to first improvement.

The mean change in the 9-point scale at Days 15 and 29 will be summarized descriptively by treatment group.

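### The SAP counts Study Day from first dose if treated and from randomization if not, so the ITT 28-day mortality window, measured from randomization, varies with any dosing delay

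*SAP*

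**What the plan says.** SAP 4.1.1 gives Day 1 two origins. For treated participants, "Day 1 is the date that the first dose of study drug (ruxolitinib/placebo) is administered to the participants". For the others, "For randomized participants not treated with any study drug, Day 1 is defined as the date of randomization".

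SAP 4.1.2 then builds Study Day on that date: "If a visit/reporting date is on or after Day 1, then the study day at the visit/reporting date will be calculated as" the date minus the Day 1 date, plus 1. Study Day 29 is therefore the Day 1 date plus 28 days.

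The primary endpoint in SAP Table 1 is "Proportion of participants who have died due to any cause through Study Day 29". It is analyzed in the ITT population, and SAP 5.3.2 says "All participants who are randomized will constitute the ITT population". Protocol 9.1.1 foresees participants who are randomized but never start treatment, so both origins can occur in the primary analysis. SAP 7.3.1 also makes anyone lost to follow-up before Day 29 non-evaluable. SAP Section 7 contains no separate Day 1 for efficacy.

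On the gap between randomization and dosing, Protocol 9.1 places screening in a 24-hour period ahead of randomization and the Day 1 assessments. Protocol Table 3 puts the eligibility check, IRT contact and first drug administration on Day 1. Neither states a maximum interval from randomization to first dose. SAP 5.3.3 nevertheless makes this a per-protocol condition: "Initiated correct randomized therapy within the Protocol-specified window".

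**The concern.** In an ITT comparison every participant's window should open at randomization and have the same length. Under the SAP clock the closing date depends on whether and when dosing began, which is settled after randomization. Two participants randomized on the same date who die on the same date can be classified differently: one first dosed a date late has a primary event on day 29 after randomization, and one who was never dosed does not.

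Evaluability shifts too. Take a participant dosed one date late, known to be alive 28 days after randomization and then lost. That participant has reached only Study Day 28 and drops out of the primary analysis. An untreated participant with identical follow-up has reached Study Day 29 and stays in. The sensitivity analysis in SAP 7.3.3 would then count the first of these as a death.

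What is at stake is the meaning of the headline 28-day mortality figure: it would not describe one fixed period from randomization.

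**Working it through.** **Inputs**
- Clock: SAP 4.1.1 and 4.1.2.
- Planning mortality: 60% placebo and 40% ruxolitinib (SAP 3.3).
- Planned pairwise size: 100 placebo and 200 ruxolitinib at one-sided 0.01436968 (SAP 3.3).
- Actual size: 211 randomized (SAP 3.3), tested at one-sided 2.5% (SAP 3.2).
- Assumed, because the documents do not give it: the delay d, the share of participants delayed, and the shape of the hazard.

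**The plan's own figure.** SAP 3.3 states about 83% power. A continuity-corrected pooled z test gives 83.7% and Fisher's exact test 83.2%, so the figure reproduces. The uncorrected pooled z test gives 86.6%, in line with the simulated 0.861–0.873 in SAP Table 2. The point here does not depend on this figure. It is only the baseline for the power comparison below.

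**Window length.** Last counted date = Day 1 date + 28. If first dose falls d dates after randomization, that is 28 + d days after randomization. If untreated, it is 28 days.

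**Mortality added per day, constant hazard.** h = −ln(1 − p)/28, and added risk = (1 − p)(1 − e^−h).
- p = 0.60: h = 0.0327; 0.40 × (1 − e^−0.0327) = 0.0129, or 1.3 points.
- p = 0.40: h = 0.0182; 0.60 × (1 − e^−0.0182) = 0.0108, or 1.1 points.

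**Range.** With cumulative hazard −ln(1 − p) × (t/28)^k, the counted mortality in a delayed participant is:

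| Delay (dates) | Window (days) | 60% rate, k = 1 | 60% rate, k = 0.7 to 1.3 | 40% rate, k = 1 | 40% rate, k = 0.7 to 1.3 |
|---|---|---|---|---|---|
| 0 | 28 | 60.0% | 60.0% | 40.0% | 40.0% |
| 1 | 29 | 61.3% | 60.9–61.7% | 41.1% | 40.8–41.4% |
| 2 | 30 | 62.5% | 61.8–63.3% | 42.1% | 41.5–42.8% |

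**Arm level, constant hazard.** If 20% of each arm are delayed one date, the rates rise by 0.26 and 0.22 points. If everyone is:
- the difference moves from 20.0 to 20.2 points;
- the odds ratio moves from 0.444 to 0.441;
- power at the planned size moves from 86.6% to 87.3%;
- power with 211 participants at one-sided 2.5% moves from 56.7% to 57.5%.

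**In deaths.** If 2:2:1 held among the 211, placebo has 211/5 = 42.2 participants and the two ruxolitinib arms together 168.8. If everyone is delayed one date, the extra counted deaths are 42.2 × 0.0129 + 168.8 × 0.0108 = 0.54 + 1.82 ≈ 2.4. If 20% are delayed, 0.2 × 2.4 ≈ 0.5. One placebo death is 1/42.2, or 2.4 points, of that arm's rate.

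**The case against.** The strongest reply is that randomization and Day 1 are meant to be almost simultaneous. Protocol 9.1 puts one 24-hour screening period before both, and the schedule places the eligibility check, IRT contact and first dose on Day 1. This largely stands: the plausible delay is 0 or 1 calendar date, and an open-ended delay would be a misreading. It does not remove the point, because that 24-hour period is independent of calendar days while Study Day is a count of dates. Randomization in the evening and a first dose the next morning already gives d = 1.

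The second reply is that inference is unharmed. A reader might infer bias between arms or an inflated type I error, but the documents do not support that. The same rule applies to every arm of a double-blind trial, so delay should be balanced, and the odds ratio barely moves. Nor are deaths between randomization and first dose lost: those participants are untreated, so their clock starts at randomization.

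Three further inferences also fail.
- SAP 7.4.2.2 says "The time from randomization to first 1- (or more) point improvement in the COVID-19 9-point ordinal scale will be derived" and censors at Study Day 29. That mixes origins, but Kaplan-Meier allows censoring times that differ by participant, and the analysis is descriptive.
- Protocol Table 10 has "Overall survival up to Day 29 determined from the date of randomization until death due to any cause", and the futility analysis in Protocol 12.5.2 also counts from randomization. Neither is a live conflict: the survival analysis is absent from SAP Table 3, and SAP 11.1 records that the futility analysis was replaced and its replacement then removed.
- The window cited in SAP 5.3.3 may simply mean the Day 1 schedule. The protocol states no explicit interval, so the reference needs reconciling, but it does not show that the per-protocol population is unusable.

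**Conclusion.** The point holds as an inconsistency in the definition of the primary endpoint and its evaluability rule, with a small expected effect. Counted mortality in a participant dosed one date late rises by about 1.3 points at the 60% rate (0.9–1.7) and about 1.1 points at the 40% rate (0.8–1.4). In a trial of 211 that is roughly 0.5 to 2.4 deaths for 20% to 100% delayed one date, and none if all were dosed on the randomization date.

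These sizes rest on the planning rates, on a constant or Weibull hazard, and on assumed delays, since the documents report neither the delays nor the number untreated. No between-arm bias, loss of type I error control or material change in power has been shown. The reason to correct it is that the labelled 28-day rate should be one fixed window from randomization in an ITT analysis.

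**What to change.** 1. In SAP 7.3.1, define the primary endpoint as death from any cause within 28 days after the date of randomization for every ITT participant, treated or not.
2. Apply that same date to the loss-to-follow-up (evaluability) rule in 7.3.1 and to the sensitivity analyses in 7.3.3, including the one that counts non-evaluable participants as deaths and the tipping point analysis.
3. Keep the first-dose clock for exposure, safety and by-visit summaries that use the pre-dose baseline in SAP 4.1.3. Moving SOFA or ordinal-scale change to a randomization clock would let Day 1 precede baseline in anyone dosed late.
4. Separately, reconcile the window cited in SAP 5.3.3 with the protocol, which states no explicit randomization-to-dose interval. What it should be is for the sponsor to state.

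The cost is SAP wording and one derived cut-off date. The date of death is collected (Protocol 9.3.1), and the date of randomization is already used in SAP 6.1.2. With first dose on or after randomization, the new window never ends later than the current Study Day 29, so no extra follow-up is needed.

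One side effect should be noted in the SAP. A death after 28 days from randomization but by Study Day 29 would still score zero event-free days under 7.4.1 without being a primary event. Reporting the distribution of time from randomization to first dose would show how many participants this touches.

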#### 4.1.2. Study Day

If a visit/reporting date is on or after Day 1, then the study day at the visit/reporting date will be calculated as

$$\text{Day \#} = (\text{visit/reporting date} - \text{Day 1 date} + 1).$$

If the visit/reporting date is before Day 1, then the study day at the visit/reporting date will be calculated as

$$\text{Day \#} = (\text{visit/reporting date} - \text{Day 1 date}).$$

A study day of -1 indicates 1 day before Day 1.

#### **4.1.3. Baseline Value**

Baseline is the last nonmissing measurement obtained before the first administration of ruxolitinib/placebo, unless otherwise defined.

For randomized participants not treated with any study drug, baseline is defined as the last nonmissing assessment before randomization for all parameters.

When scheduled assessments and unscheduled assessments occur on the same day and the time of the assessment or time of first dose is not available, use the following convention to determine baseline:

- If both a scheduled and an unscheduled visit are available on the day of the first dose and the time is missing, use the scheduled assessment as baseline.
- If all scheduled assessments are missing on the day of the first dose and an unscheduled assessment is available, use the unscheduled assessment as baseline.

#### **4.1.4. Last Available Value**

The last available value is the last nonmissing measurement obtained after starting ruxolitinib/placebo and within 31 days after the last dose of ruxolitinib/placebo.

#### **4.1.5. Handling of Missing and Incomplete Dates and Times**

In general, values for missing dates will not be handled unless methods for handling missing dates are specified in this section or relevant sections. The original reported dates collected on the eCRF should be used in all relevant listings. The following rules will be used for handling partial dates for analyses requiring dates.

When calculating the time since diagnosis, a partial date will be treated as missing and a time will not be calculated. When calculating the time since intubation, a partial date and/or 24-hour time will be treated as missing and a time will not be calculated.

When the date of the last dose is used in deriving variables such as duration of treatment or TEAE flag, a missing or partial date of the last dose will be handled as follows:

- If only the day is missing, then the earlier date of the last day of the month or the date that the participant discontinued treatment will be used.
- Otherwise, the date that the participant discontinued treatment will be used as the date of the last dose.

For relevant efficacy endpoints, a partial date of the death date will be handled as follows in the calculation:

- If mmyyyy for the last known alive date = mmyyyy for the death date, then the death date will be set to the day after the last known alive date.
- If mmyyyy for the last known alive date < mmyyyy for the death date, then the death date will be set to the first day of the death month.
- Otherwise, the partial death date will not be imputed.

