- ^g Vital signs will be collected once daily while hospitalized between 7:00 AM and 12:00 PM local time and include heart rate, respiratory rate, systolic and diastolic blood pressure, and body temperature. Not required after discharge.
- ^h Arterial blood gases will be collected during screening, within 6 hours of planned randomization, to assess PaO₂/FiO₂. Thereafter, ABGs will be performed daily while 1) the participant is receiving mechanical ventilation, OR 2) the participant has an arterial line. Parameters including pH, PaO₂, PaCO₂, and SaO₂ will be collected for each ABG. SpO₂ (pulse oximetry) will be recorded in the eCRF once daily while hospitalized. ABGs and SpO₂ not required after discharge.
- ¹ Ventilator settings (as applicable) will be collected once daily between 7:00 AM and 12:00 PM local time. Settings to be collected include mode, FiO₂, PEEP, VT, and respiratory rate. Dates of intubation and extubation (if applicable) will be recorded. Supplemental oxygen support post-extubation will be collected daily through Day 29, until hospital discharge.
- ^j If participant is discharged, a telephone call may be used to perform assessment. See Appendix B for scale.
- ^k Beginning at Day 15, the participant may continue treatment up to Day 28 at the discretion of the investigator and after approval by the sponsor medical monitor.
- ¹ Hematology, clinical chemistry, and markers of inflammation should be measured by the local laboratory. See Section 9.4.3 for required analytes. If participant is discharged, local laboratory assessments may be performed on Day 15 and/or Day 29 if feasible.
- ^m An optional serum sample will be collected at Day 1 (predose) and Day 7 and 15 for cytokine analysis. See Section 9.5.1 for collection, processing, storage and shipment instructions.
- ⁿ Pregnancy test: only for females of childbearing potential, serum pregnancy test (serum hCG) will be performed at screening assessment. Serum or urine test is acceptable at subsequent assessment(s).
- ° Screening chest imaging may be ≤ 2 days prior to Day 1.

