#### 6.1.2. Baseline Disease Characteristics and Disease History

The following baseline disease characteristics will be summarized for the ITT population: predefined coexisting disorders, baseline SOFA score, baseline COVID-19 9-point ordinal scale clinical status, baseline ARDS severity (severe [ $\text{PaO}_2/\text{FiO}_2 \leq 100$ ] vs mild/moderate [ $\text{PaO}_2/\text{FiO}_2 > 100$  and  $\leq 300$  mmHg]), ARDS severity at randomization, time (in hours) from start of mechanical ventilation to randomization, time (in days) from initial diagnosis to randomization, time (in days) from hospital admission to randomization, baseline CRP ( $\leq 100$  mg/L or  $> 100$  mg/L), baseline D-dimer ( $\leq 1000$  ng/mL or  $> 1000$  ng/mL), baseline ferritin ( $\leq 300$  ng/mL or  $> 300$  ng/mL), BMI at baseline ( $\geq 30$  or  $< 30$ ), prior or concomitant remdesivir, prior or concomitant convalescent plasma, prior or concomitant corticosteroid, concomitant anti-coagulant, prior biologic, prior or concomitant neutralizing antibodies, and prior or concomitant corticosteroid with prior or concomitant remdesivir.

Time from initial diagnosis will be calculated as follows:

$$\text{Time since diagnosis (days)} = (\text{date of randomization} - \text{date of diagnosis} + 1).$$

Time from start of mechanical ventilation will be calculated as follows:

$$\text{Time from start of mechanical ventilation (hours)} = (\text{date and time of randomization} - \text{date and time of intubation}).$$

Time from hospital admission to randomization will be calculated as follows:

$$\text{Time from hospital admission (days)} = (\text{date of randomization} - \text{date of hospital admission} + 1).$$

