### 7.3.2. Subgroup Analyses for Primary Endpoint

Subgroups will be formed based on the following participant characteristics and baseline variables for those participants whose data are available:

- ARDS severity: severe ( $\text{PaO}_2/\text{FiO}_2 \leq 100$  mmHg) versus mild/moderate ( $\text{PaO}_2/\text{FiO}_2 > 100$  and  $\leq 300$  mmHg)
- Gender: male or female
- Age group:  $< 18$  years, 18-64 years, or  $\geq 65$  years
- Baseline CRP:  $\leq 100$  mg/L or  $> 100$  mg/L
- D-dimer at baseline:  $\leq 1000$  ng/mL or  $> 1000$  ng/mL
- Ferritin at baseline:  $\leq 300$  ng/mL or  $> 300$  ng/mL
- Race: White/Caucasian, Black/African-American, Asian, American-Indian/Alaska Native, Native Hawaiian/Pacific Islander, or Other
- Ethnicity: Hispanic/Latino, Not Hispanic/Latino, or Other
- Hours of mechanical ventilation at baseline:  $\leq 48$  hours or  $> 48$  hours
- BMI at baseline:  $\geq 30$  or  $< 30$
- Prior or concomitant remdesivir: yes or no
- Prior or concomitant convalescent plasma: yes or no
- Concomitant anticoagulant use: yes or no
- Concomitant corticosteroid use: yes or no
- Prior biologic use: yes or no

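### Participants with a complete intubation date but no clock time drop out of the 48-hour ventilation subgroup even when the dates alone settle their category

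*SAP*

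**What the plan says.** SAP 6.1.2 lists "time (in hours) from start of mechanical ventilation to randomization" among the baseline disease characteristics. It derives the value as date and time of randomization minus "date and time of intubation".

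SAP 4.1.5 governs incomplete values: "When calculating the time since intubation, a partial date and/or 24-hour time will be treated as missing and a time will not be calculated". Because of the and/or, a missing clock time is enough to block the calculation when the date is complete. The same section sets the default: "In general, values for missing dates will not be handled unless methods for handling missing dates are specified in this section or relevant sections".

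SAP 7.3.2 then uses "Hours of mechanical ventilation at baseline" to form two subgroups for the primary endpoint, with the cut at 48 hours. Subgroups are formed on "baseline variables for those participants whose data are available". Neither section offers a way to assign the category from dates. Protocol 12.4.1 lists the same subgroup.

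On data collection, the ventilator/oxygen footnote to Protocol Table 3 says "Dates of intubation and extubation (if applicable) will be recorded". It does not mention a clock time.

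**The concern.** Inclusion criterion 4 (Protocol 6.1) requires current intubation but puts no limit on how long the patient has been ventilated. Of the 15 subgroup variables in SAP 7.3.2, this is the only one that addresses when treatment starts relative to intubation. A rule that discards participants whose category is certain therefore weakens the plan's one subgroup look at that question, and does so for no gain.

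The final analysis has 211 participants (SAP 3.3). At 2:2:1 the placebo group is about 211 / 5 = 42, divided between two ventilation-time categories, so each lost participant costs some precision. Protocol 12.4.1 also allows a subgroup to be dropped if a category has fewer than 10 participants, and avoidable missing values bring that closer.

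The rule is also out of step with the rest of the SAP. The same section places a partial death date using the last known alive date. SAP 4.2.2 and 9.2.1 classify medications and adverse events by what can be established for certain.

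**Working it through.** The plan states no figure on this point, so there is none to reproduce. The check has two parts: what the calendar dates imply, and an illustration of size.

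**Step 1. Bounds from dates alone.** Let d = randomization date minus intubation date in calendar days, and let t_R and t_I be the two clock times in hours, each from 0 to just under 24. Then

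elapsed hours = 24d + (t_R − t_I),

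which lies strictly between 24(d − 1) and 24(d + 1). Intubation precedes randomization, so the value cannot be negative. To the minute:

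| d (days) | Shortest (h) | Longest (h) | Category at 48 h |
|---|---|---|---|
| 0 | 0.00 | 23.98 | at most 48, certain |
| 1 | 0.02 | 47.98 | at most 48, certain |
| 2 | 24.02 | 71.98 | undetermined |
| 3 | 48.02 | 95.98 | more than 48, certain |
| 4 | 72.02 | 119.98 | more than 48, certain |

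Larger d moves further above 48. The bounds assume that both dates are on the same local clock.

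**Step 2. Can d = 2 be rescued by the randomization time?** No. At d = 2 the interval is at most 48 hours exactly when t_I is at or after t_R. With t_R known and t_I unknown, both outcomes stay possible for 1,439 of the 1,440 minutes of the day. The exception is randomization at 00:00. Treating d = 2 without a time as missing is therefore right.

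**Step 3. What the SAP does instead.** With a complete date and no time, hours are not calculated (SAP 4.1.5), the only stated derivation needs the time (SAP 6.1.2), and the subgroup takes available data (SAP 7.3.2). The participant is unclassified at every value of d, including those where Step 1 gives a certain answer.

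**Step 4. Illustrative size.** The documents give neither the share without a clock time (m) nor the share of those at d = 2 (q). Both are assumed here.

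- Unclassified under the SAP rule = 211 × m.
- Placed by dates = 211 × m × (1 − q).
- m = 5%: 211 × 0.05 = 10.6 unclassified. Placed: 7.4 at q = 30%, 9.5 at q = 10%.
- m = 30%: 211 × 0.30 = 63.3 unclassified. Placed: 44.3 at q = 30%, 57.0 at q = 10%.
- m = 0: nobody is affected.

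Across m of 5% to 30%, about 11 to 63 would be unclassified and dates would place about 7 to 57. If times are nearly always recorded, both numbers approach zero.

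**The case against.** The strongest objection is that the situation may hardly arise. The Table 3 footnote mentions dates but does not exclude times. The SAP was written against CRFs approved on 30 SEP 2020 (SAP 2.1), after the protocol amendment of 02 JUN 2020. Its formula uses a time of intubation, and its missing-data rule refers to a 24-hour time. Both suggest that the eCRF has a time field. That stands: the frequency is unknown and could be negligible.

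Three stronger readings are tempting, and the documents support none of them.

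- **That nobody can be classified because sites record dates only.** This turns the footnote's silence about time into a statement, and it fits poorly with SAP 4.1.5 and 6.1.2. The CRF that would settle it is not among the documents.
- **That the longer-ventilated group is depleted selectively, biasing the comparison.** Times may be missing more often for patients intubated before a transfer, but neither document discusses this. Intubation precedes randomization and the trial is double-blind (Protocol 7.4), so there is no evident reason for missing times to differ by arm.
- **That the baseline table loses people whose category is known.** SAP 6.1.2 summarizes this variable in hours and gives no 48-hour cut. Without a clock time the hours are unknown, so leaving them missing is correct.

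It is also fair to say that an available-data rule for an incomplete baseline covariate is conventional, that the exclusion follows from reading three SAP sections together, and that this is one of 15 subgroup variables with no multiplicity adjustment. These points limit the importance. They do not justify discarding a category that is certain.

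**Conclusion.** The point holds as a small, avoidable loss of information. When the intubation date is complete and the time is absent, the SAP leaves the 48-hour category empty, although differences of 0, 1, or 3 or more days fix it exactly. That conclusion rests on calendar arithmetic and on the three SAP sections read together. It does not depend on the illustrative counts.

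The effect is confined to the precision and completeness of one pre-specified subgroup analysis of 28-day mortality. The primary model (SAP 7.3.1) and the sensitivity analyses (SAP 7.3.3) do not use the variable, and the continuous-hours summary is handled properly. No bias between arms is shown. The number of participants affected is unknown, from none upward. This is an optional improvement, worth making because it is nearly free.

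**What to change.** Leave the SAP 4.1.5 rule in place for the continuous hours variable, and add for the subgroup:

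*For the 48-hour ventilation category, if the intubation date is complete but the time is missing, assign at most 48 hours when the randomization date minus the intubation date is 0 or 1 day, and more than 48 hours when it is 3 or more days. Leave the category missing only when the difference is exactly 2 days.*

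This is classification from known dates. It imputes nothing and adds no assumption beyond both dates being on the same local clock. It would also help to report the number left unclassified in each arm, so that the reader can see whether the issue arose.

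The cost is one SAP sentence and a few lines of code, settled before unblinding. It needs no data beyond dates already collected.
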